3.2. General Methods

All data listings that contain or imply an evaluation date will contain a relative study day (Rel Day). Pre-treatment and on-treatment study days are numbered relative to the day of the first dose of study medication which is designated as Day 1. The preceding day is Day -1, the day before that is Day -2, etc. Post-treatment study days are numbered relative to the first dose and are designated as Day 1, Day 2, etc. for table and listing display. Data for time interval analysis and graphing will be displayed as days since dosing where Hour 6 timepoint on Day 1 is converted to 0.25 days.

All outputs will be incorporated into Microsoft Word or Excel files, or Adobe Acrobat PDF files, sorted and labeled according to the International Conference on Harmonisation (ICH) recommendations, and formatted to the appropriate page size(s).

Tabulations will be produced for appropriate demographic, baseline, immunogenicity, and safety parameters. For categorical variables, summary tabulations of the number and percentage of subjects within each category (with a category for missing data) of the parameter will be presented. For continuous immunogenicity variables, the number of subjects, geometric mean, median, geometric standard deviation (SD), minimum, and maximum values will be presented.

Other continuous variables (e.g., BMI) will be summarized by the number of subjects, mean, median, SD, minimum, and maximum values. Summarizations will be tabulated by treatment group.

Formal statistical hypothesis testing will be performed on the primary and secondary immunogenicity endpoints with all tests conducted at the 2-sided, 0.05 level of significance. Summary statistics will be presented, as well as CIs on selected parameters, as described in the sections below.

3.3. Computing Environment

All descriptive statistical analyses will be performed using SAS statistical software Version 9.4, unless otherwise noted. Medical history and adverse events will be coded using the Medical Dictionary for Regulatory Activities (MedDRA) Version 26.1. Concomitant medications will be coded using the World Health Organization (WHO) Drug Dictionary Version Global B3 Sep 2023.

3.4. Baseline Definitions

For all analyses, baseline will be defined as the most recent measurement prior to administration of study vaccine.

3.5. Methods of Pooling Data

In addition to presenting results by PHV01 vaccine dose levels, data will be pooled across PHV01 vaccine dose levels for analyses as an PHV01 overall group and all placebo subjects will be pooled as another group.

3.6. Adjustments for Covariates

Additional exploratory analyses adjusted for covariates may be performed on an ad-hoc basis.

3.7. Multiple Comparisons/Multiplicity

No adjustments will be made for multiplicity. Study objectives will be evaluated through a combination of statistical and clinical assessments, which is not consistent with an approach to adjust for multiple comparisons.

3.8. Subpopulations

The immunologic endpoints will be analyzed separately for males and females, and by age group (< 40 and ≥ 40 years old).

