7.5.4. Subgroup Analysis

Multivariable logistic regression may be used to evaluate the association between age, sex, race, and seroconversion rate.

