3. GENERAL STATISTICAL METHODS

3.1. Sample Size Justification

The sample size for this Phase 1 study (N=36 subjects; total N=10 per vaccine dose level [30 vaccinees and 6 placebo]) was selected to provide initial data and obtain estimates of safety and immunogenicity parameters and their respective variabilities. Group size is based on prior experience with ERVEBO safety studies and assumptions from the responses seen in the preclinical studies. This Phase I study is therefore designed with the goal of providing further information for better planning of future in-human studies. As this is a FIH study of PHV01, the sample size was established to provide reasonable information for descriptive purposes and not specifically designed for formal hypothesis testing.

Safety: With a sample size of 10 subjects, an upper bound of 30.9% is established for the 2-sided 95% confidence interval (CI) for the incidence of an AE in the case that the event is not observed according to the two-sided 95% (Clopper-Pearson) exact CI. Alternatively, when pooled together all 30 vaccinees, an upper bound of 11.6% is provided. This established the sample sizes needed to ensure minimal AE rates could be detected with confidence.

Immunogenicity: Clinical data for the rVSV-ZEBOV-GP Ebola vaccine showed that a dose of 3×10^6 pfu/mL yielded a Day 29 GMT IgG ELISA titer of 1400 EU/mL and geometric standard deviation (SD) of 3.3. Assuming that the variability in responses to PHV01 is similar, the proposed group sizes afford 80% (alternate 90%) power to detect a 6.4-fold (alternate 8.6-fold) increase, comparing geometric mean ELISA titer using a two-sided test with alpha=0.05 for each vaccine group with the placebo group. Alternatively, performing the same comparison against placebo by pooling all three treatment groups with a total 30 vaccinated subjects, we would have 4.7-fold and an alternate 5.9-fold with 80% and 90% power, respectively.

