4.3. Immunogenicity Evaluation

Immunogenicity analyses will be conducted using the PP population. Supportive analyses of immunogenicity will be based on the mITT population if the number of subjects excluded from PP population is more than 10%.

4.3.1. Geometric Mean Titers and Mean Fold Increase of IgG ELISA Antibody and Neutralizing Antibody PsVNT

For IgG ELISA antibody titers and neutralizing antibody titers PsVNT (PsVNT₅₀ and PsVNT₈₀), GMT, and 95% confidence limit will be provided on Days 1, 8 (if tested), 15, 29, 85, and 181, where the GMT is calculated as the anti-log of the base-2 log transformed mean and the same for the corresponding confidence limit. Results will be presented by treatment group along with a combined PHV01 group, and the descriptive statistics will include the GMT, the geometric standard deviation, 25th percentile, median, 75th percentile, minimum, and maximum values. If appropriate, the analyses will be repeated for the GMT using the anti-log of the base-10 log transformed mean.

Pairwise comparison of the above antibody titer levels for each PHV01 dose level to one another and to the placebo group, as well as the comparison of the combined PHV01 dose group relative to the placebo group will be performed with Satterthwaite t-tests. T-tests will be performed on log-2 transformed values and the resulting estimated mean difference and associated 95% CI will then be back transformed using base-2 antilogarithms to obtain estimates

on the ratio scale. If appropriate, the analyses will be repeated using base-10 log transformed values and back transformed using base-10 antilogarithms to obtain estimates. In the event of extreme outliers or non normally distributed data, Wilcoxon rank-sum test may be performed to support the comparison.

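### SAP 3.8 looks at age only by separate analyses either side of 40, which does not test whether antibody response differs by age; one exploratory model with continuous age would

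*SAP*

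**What the plan says.** SAP 3.8 (Subpopulations) reads: "The immunologic endpoints will be analyzed separately for males and females, and by age group (< 40 and ≥ 40 years old". It gives no reason for the cut at 40, no minimum group size and no comparison of one age group with the other.

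The titer methods in SAP 4.3.1 are Satterthwaite t-tests and ANOVA by treatment group, beginning with "Pairwise comparison of the above antibody titer levels for each PHV01 dose level to one another and to the placebo group". Age does not appear in them. The repeated-measures models in Protocol 7.5.2 concern dose and time and do not mention age either. SAP 4.3.2 names a repeat of the seroconversion analysis by sex, but none by age.

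Two other provisions touch on age or covariates. SAP 3.6 says "Additional exploratory analyses adjusted for covariates may be performed on an ad-hoc basis", naming no covariate, outcome or model. Protocol 7.5.4 says "Multivariable logistic regression may be used to evaluate the association between age, sex, race, and seroconversion rate". That model is optional, has a yes/no outcome, and is not carried into the SAP.

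Randomization is stratified by sex and not by age (Protocol 3.3.1). Eligible ages run from 18 to 60 (Protocol 1.8).

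**The concern.** Comparing dose with placebo inside each age group answers whether the vaccine raised titers in that group. It does not answer whether response changes with age, which is the usual reason for an age subgroup. A significant result on one side of 40 and a non-significant one on the other can easily be misread as an age effect, when the difference between the two was never estimated.

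The split also roughly halves groups that are already small. Cutting age discards information within each side of 40, and chance imbalance in age could leave one side with too few placebo subjects for the planned test. At stake is a secondary description of how response varies with age, in data that could support a more direct and more informative estimate.

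**Working it through.** **Inputs.** Group sizes are 10 per dose, 30 vaccinees in all, and 6 placebo (SAP 3.1). Variability is a "geometric standard deviation (SD) of 3.3", so the SD on the natural-log scale is ln 3.3 = 1.194. Tests are two-sided at 0.05. The enrolled age distribution and the size of any age effect are not in the documents and are assumed below.

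**1. The plan's own figure.** SAP 3.1 claims "80% (alternate 90%) power to detect a 6.4-fold (alternate 8.6-fold) increase". For a pooled two-sample t-test, SE = 1.194 × √(1/n₁ + 1/n₂), and power comes from the noncentral t with noncentrality ln(fold)/SE.

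- 10 v 6: SE = 1.194 × √(1/10 + 1/6) = 0.617. At 6.4-fold the noncentrality is 1.856/0.617 = 3.01 on 14 df, giving 79.9% power. Solving for 80% and 90% gives 6.41-fold and 8.59-fold.
- 30 v 6: 4.66-fold and 5.94-fold.

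Both agree with the SAP, so the method and variance are the plan's own.

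**2. The same comparison inside one age half.** An even split gives 5 v 3.

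- SE = 1.194 × √(1/5 + 1/3) = 0.872. At 6.4-fold the noncentrality is 1.856/0.872 = 2.13 on 6 df, giving 43% power.
- The fold detectable with 80% power is 18.8.
- By simulation, the Satterthwaite test that SAP 4.3.1 specifies has about 37% power at 6.4-fold, against about 77% with the full 10 v 6.
- All vaccinees against placebo becomes 15 v 3. The detectable fold rises from 4.7 to 9.5, and power at 4.7-fold falls from 80% to 49%.

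**3. Chance that the placebo side of the test is undefined.** The Satterthwaite test needs a variance, hence at least two subjects, in each group. Treat the 6 placebo ages as independent, with a share p below 40. The chance that one half holds at most 1 placebo subject is P(X ≤ 1) + P(X ≥ 5), with X binomial(6, p).

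- p = 0.5: 2 × (1 + 6)/64 = 14/64 = 22%.
- p = 0.7: P(X ≤ 1) = 0.3⁶ + 6 × 0.7 × 0.3⁵ = 0.011, and P(X ≥ 5) = 0.7⁶ + 6 × 0.3 × 0.7⁵ = 0.420. The sum is 43%.

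**4. Continuous age against age cut at 40.** Assume ages uniform on 18 to 60.

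- The variance of age is 42²/12 = 147.
- The share below 40 is 22/42 = 0.524, and the two halves' mean ages, 29 and 50, differ by 21 years. The cut therefore captures 0.524 × 0.476 × 21² = 110.
- The information kept is 110/147 = 75%.

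Power was simulated for 30 vaccinees with residual SD ln 3.3 and no dose effect, in a linear model adjusted for dose and sex:

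| Fall in titer from age 18 to 60 | Continuous age | Age cut at 40, same model | Gain (points) |
|---|---|---|---|
| 4-fold | 38% | 30% | 8 |
| 6-fold | 56% | 43% | 13 |
| 8-fold | 70% | 55% | 15 |

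The middle column is generous to the plan, since the SAP contains no such pooled model. A 6-fold fall over 42 years is 6^(10/42) = 1.53-fold per 10 years.

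**The case against.** **Age is not an objective.** No objective or endpoint mentions it. SAP 3.1 calls the sample size descriptive and not designed for formal testing. The Day 29 interim analysis that guides Phase 2 dose selection is by treatment group, with no age subgroup. All of this stands and limits the importance of the point, although SAP 3.2 does plan formal tests on the primary and secondary immunogenicity endpoints.

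**A rerun of every test by age is not written.** SAP 3.8 says only that endpoints are analysed separately, and Section 4.3 spells out a repeat by sex alone. The 5 v 3 figures therefore depend on a reading, if the natural one. The absence of any comparison between age groups does not depend on it.

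**The proposed model is not powerful either.** At 38% power it would miss a 4-fold fall more often than not. This also stands. The gain is a direct estimate of the age effect with an interval, more than a reliable test.

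**Undefined tests are a risk only.** The risk depends on who enrols. Newcombe intervals for rates can still be computed with a single subject, and the main analyses are unaffected.

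**A stronger reading about the logistic model fails.** A reader might infer that the seroconversion model in Protocol 7.5.4 could often not be fitted because nearly all vaccinees would respond. The documents do not support this. The 1400 EU/mL mean in SAP 3.1 belongs to the Ebola vaccine at one dose, and only its variability is carried over to PHV01. The assay's lower limit of quantitation is not stated. The model is not restricted to vaccinees, so placebo non-responders could enter it. Nor does it cut age: it reduces the outcome to yes or no, and that outcome is a named secondary endpoint.

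**Conclusion.** The point holds as a minor refinement of a planned subgroup analysis. SAP 3.8 does not test whether response differs by age, and nothing prespecified relates continuous age to log titer; the unnamed ad hoc analyses of SAP 3.6 do not fill that gap.

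If the Section 4.3 tests are rerun within each half, the detectable fold about triples (18.8/6.4 = 2.9). Keeping age continuous in one model recovers roughly 8 to 15 points of power compared with cutting it.

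The power figures rest on the plan's geometric SD of 3.3 and, for the age model, on uniform ages, a log-linear age effect and no dose effect. The undefined-test figures rest on an assumed share below 40. It would go too far to say that real age effects will be missed or that the planned tests cannot be computed: they are more likely to be missed, and some tests may turn out to be undefined.

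**What to change.** In SAP 3.8, prespecify one exploratory linear model per assay (ELISA, PsVNT50, PsVNT80). The response is log2 Day 29 titer in vaccinees, and the terms are dose group, sex and age as a continuous variable. Report the GMT ratio per 10 years of age with its 95% CI as the main output, since power is modest.

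Present the under-40 and 40-and-over results descriptively (GMTs, rates and confidence intervals), and say explicitly that the Section 4.3 tests are not repeated within age groups. Leave the optional seroconversion model in Protocol 7.5.4 in place.

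The cost is a few sentences in the SAP and three extra models, with no new data. The downside is the assumption that log titer is linear in age, which a scatter plot of log titer against age, read with the descriptive age-group table, can check.

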3.9. Withdrawals, Dropouts, Loss to Follow-up

To ensure that a required minimum number of subjects (36) are available for vaccination, any subject scheduled for vaccination who is not available at time of vaccination will be replaced

with a screened and eligible alternate subject. If the replacement occurs after randomization, the replacement subject will be randomized to the same treatment group. Once vaccinated, up to 3 subjects may be replaced should they be withdrawn from the study or lost to follow-up before Day 29.

3.10. Missing, Unused, and Spurious Data

In general, there will be no substitutions made to accommodate missing data points. All data recorded on the case report form will be included in data listings that will accompany the CSR.

Subjects with negative post-baseline antibody response (defined as the corresponding titers < LLOQ) will have a titer value assigned as LLOQ/2.

When tabulating AE data, partial dates will be handled as follows. If the day of the month is missing, the onset day will be set to the first day of the month unless it is the same month and year as study treatment. In this case, in order to conservatively report the event as treatment-emergent, the onset date will be assumed to be the date of treatment. If the onset day and month are both missing, the day and month will be assumed to be January 1, unless the event occurred in the same year as the study treatment. In this case, the event onset will be coded to the day of treatment in order to conservatively report the event as treatment-emergent. A missing onset date will be coded as the day of treatment.

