AEs will be recorded starting with Screening. Once dosed, subjects will also be monitored for the occurrence and severity of indicators of reactogenicity. Treatment-emergent AEs (TEAEs) include all AEs that occur with and after dosing. It is expected that PHV01 may cause cytokine-mediated acute phase reactions similar to those associated with the similar Ebola vaccine (ERVEBO) during the first 1-3 days after inoculation (17). Thus, TEAEs will be solicited daily for 14 days after vaccination using a scripted questionnaire or Memory Aid (Section 5.4.1), including expected local and systemic AEs, as well as specific neurologic, joint, or dermatologic AEs, and unsolicited AEs; solicited AEs for Days 16-29 are limited to instances of neurological signs and symptoms, arthritis, and rash. Throughout the remainder of the study (e.g., until study day 181), subjects will be asked to report important changes in health status and concomitant medications, as well as any medically attended adverse events (MAAEs) (Section 5.4.2). AEs will be recorded throughout the rest of the study if noted on subsequent Memory Aids or if evaluated as MAAEs, serious AEs (SAEs), or AEs of special interest (AESIs), along with any concomitant medications (Section 6.4.3). The severity of all AEs will be graded in accordance with the FDA document "Guidance for Industry: Toxicity Grading Scale for Healthy Adult and Adolescent Volunteers Enrolled in Preventive Vaccine Clinical Trials" (APPENDIX 1).

Medically-Attended Adverse Events

Any AEs that cause a subject to seek medical care (including extra visits to the clinical site) are considered to be MAAEs. These will be recorded for the entire study. Subjects will be asked to record MAAEs on Memory Aids that will be reviewed during the visits on days 29, 85, and 181.

Adverse Events of Special Interest

In order to maximize the value of vaccine safety data in clinical trials, the CEPI and the Brighton Collaboration have formed an international organization, "Safety Platform for Emergency Vaccines" (SPEAC), to promote standardization of data collection, presentation, and analysis of AESIs relevant to vaccines in general, to specific vaccine platforms (live virus vaccines, rVSV vaccines), and in specific cases to the target disease itself (28).

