Hematology, chemistry, and coags (10.7 mL) ⁸	X	X		X	X		X		
HLA-B27 Testing		X							
Urinalysis ⁹	X			X	X		X		
MARV antibody tests (2 x 10 mL) ¹⁰		X			X	X	X	X	X
Blood for research (100 mL) ¹¹								X	
PBMC/T-cell Assay ¹²		X			X		X		
Transcriptomics (2.5mL PaxGene RNA tube) ¹³		$X \times 2$	X	X	X	X			
MARV viremia (7 mL) and shedding ¹⁴		$X \times 2$	X	X	X	X	X		
Cytokine levels (10mL) ¹⁵		X		X	X		X		
Vaccination		X							
Post-vaccination observation ¹⁶		X							
Provision of emergency contact card		X							
Training and review of Memory Aid		X	X	X	X	X	X	X	X

Abbreviations: AESI = Adverse Event of Special Interest; eCRF = electronic case report form; HBsAg = hepatitis B surface antigen; HCG = human chorionic gonadotropin; Hct = hematocrit; HCV = hepatitis C; HepB = hepatitis B; HgB = hemoglobin; HIV = human immunodeficiency virus; INR = international normalized ratio; MAAE = medically attended adverse event; RBC = red blood cell; PBMC = peripheral blood mononuclear cell; PCR = polymerase chain reaction; PT = prothrombin time; PTT = partial thromboplastin time; SAE = serious adverse event; TEAE = treatment emergent adverse event; WBC = white blood cell.

Footnotes:

- ¹ Obtain written informed consent for participation in the clinical study, clinical samples, and HIV testing.
- ² Demographic data include age, height and weight (for BMI), race, and ethnicity.
- ³ Vital signs will include blood pressure and pulse while seated and at rest, and body temperature measured orally. On Visit 2, vital signs will be assessed up to 60 minutes before vaccination, then at 60-90 minutes after vaccination and at $6h \pm 1h$. (Shown as $X \times 2$)
- ⁴ Directed physical examination at discretion of Investigator. See the Protocol for the Arthritis Pathway algorithm for subjects with joint complaints. If rash is present on any visit, the PI should reference the Dermatology Pathway.
- ⁵ SAEs, MAAEs, and AESIs will be recorded from day of consent until EOS. AEs will be recorded beginning with Screening. All TEAEs will be recorded from dosing on day 1 through day 29, and during the rest of the study. Concomitant medications will be recorded up to 6 months prior to study entry and throughout the duration of the study. This will include dietary supplements and other prophylactic substances.
- ⁶ Pregnancy tests (serum HCG) will be done in all female subjects at Screening. Repeat pregnancy tests (urine) will be done in all female subjects prior to vaccination and at day 29.

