5.1.1. Screening Visit

Visit 1/Screening (days -28 to -1)

Reconfirm interest in this study before starting; significant time and travel is required in the first month and multiple resources are committed by the site and Sponsor to each subject.

Screening and enrollment procedures will be the same for all potential subjects. Any potential subject falling outside the 28-day window will require rescreening. The following procedures will be performed during the screening/briefing visit:

- Explain the study and review the informed consent with subject. Obtain written informed consent for participation in the clinical study and for HIV testing. Provide a copy of the signed ICF to the subject.
- Collect demographic information and medical history (including concomitant medications).
- Check each inclusion and exclusion criterion.
- Weight, vital signs, and physical examination, including baseline neurologic examination
- Sample collection including:
 - o Complete blood count (CBC) with WBC differential
 - o Coagulopathy tests, including prothrombin time (PT), partial thromboplastin time (PTT), and international normalized ratio [INR]
 - o Serum chemistry metabolic panel, including at a minimum creatinine, glucose, AST, ALT, and total bilirubin (plus direct bilirubin if elevated)
 - o Pregnancy test (serum) (all female subjects who may become pregnant see below)
 - Urinalysis
 - o Viral serologies (HIV-1, HIV-2, hepatitis C [HCV], hepatitis B surface antigen [HBsAg])

Potential subjects will be notified of their eligibility as soon as laboratory results are available and an assessment can be made by the Investigators. If determined to be eligible, subjects will be scheduled for their initial vaccination (day 1, Visit 2).

Regardless of eligibility, individuals will be informed of any significantly abnormal test results in an expeditious manner via telephone, in person, or by written communication. Appropriate counseling will be given regarding necessary medical follow-up. Participants may rescreen once.

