5.1.2. Treatment Visit

Visit 2/Enrollment and Injection (day 1)

Subjects will have only 1 dosing visit during the study. Each subject will receive a 1 mL IM injection of PHV01 or placebo into the outer aspect of the subject's upper arm (deltoid area).

The following procedures will be performed during the injection visit, prior to the injection:

- Vital signs check
- Review of inclusion/exclusion criteria to confirm eligibility, then randomize
- Review of any AEs (including concomitant medications) since previous visit
- Directed physical examination (including proposed injection site)
- Rapid antigen test for SARS-CoV-2
- Urine pregnancy test (females only)
- Human leukocyte antigen (HLA) B27 typing (once only)
- Hematology, chemistries, and coagulation tests as above
- Collection of baseline samples for:
 - o PHV01 antibody, including sera for rheumatology and dermatology assessments
 - o PBMCs
 - o Transcriptomics
 - o Vaccinemia
 - Cytokines levels

Injection Procedures

- Administration of PHV01 or placebo
- Provision of emergency contact card
- Post-injection observation period: examination of injection site and vital signs check (≥60 minutes and ≤90 minutes post-vaccination)
- Explanation of the Memory Aid (see Section 5.4), distribution of thermometer and ruler, and review of use. Subjects are to record the severity of symptoms, including injection site reactions, joint-related AEs (joint pain, pain on motion of joints, joint swelling, joint tenderness), neurological issues, and rash, with the concomitant medications taken, and body temperature.

Subjects will remain in the clinic on day 1 for lunch and a blood draw at $6h \pm 1h$, including;

- Vital signs check
- Review of any immediate AEs or change in health status
- Collection of samples for vaccinemia, shedding, and transcriptomics

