- Gastrointestinal Symptoms (symptoms include nausea, vomiting, abdominal pain, and diarrhea) [CRF terms: Nausea, Vomiting, Abdominal Pain, Diarrhea]
- Mucosal Lesions [CRF terms: Mucosal Lesion, Mouth Ulcer]
- Skin Lesions [CRF terms: Skin Lesion]
- Neurological Symptoms (symptoms include blurry vision, changes in balance or coordination, confusion, disorientation, dizziness, severe headache, shaking or body tremors, slurred speech, tingling or numbness, weakness or feeling weak) [CRF terms: Blurry Vision, Changes in Balance or Coordination, Confusion, Disorientation, Dizziness, Severe Headache, Shaking or Body Tremors, Slurred Speech, Tingling or Numbness, Weakness or Feeling Weak]

Neurological symptoms described above will be considered as solicited neurological AEs. Specific joint related (arthralgia, joint swelling, and joint tenderness) will be considered as solicited rheumatologic AEs; and mouth ulcer or skin/mucosal lesions will be considered as dermatologic AEs.

All TEAEs that cause a subject to seek medical care (including extra visits to the clinical site) are considered to be MAAEs.

Additionally, certain neurologic/hematologic/immunologic diseases are considered as AESIs in the study. Such AESIs include pneumonitis, acute respiratory distress syndrome, multiorgan failure, a hemorrhagic diathesis, certain neurologic events (encephalitis, myelitis, aseptic meningitis, optic neuritis, transverse myelitis, generalized convulsions, Guillain-Barré Syndrome, acute disseminated encephalomyelitis), thrombocytopenia ≥ Grade 2, anaphylaxis, and vasculitides.

Summary tables will be generated for the following:

- Solicited local site AEs within 7 days, and 8 to 14 days following vaccination by Solicited Term and severity
- Solicited systemic AEs within 7 days, and 8 to 14 days following vaccination by Solicited Term and severity
- Solicited neurological AEs within 7 days, 8 to 14 days, 15 to 28 days and up to day 181 following vaccination by Solicited Term and severity
- Unsolicited AEs within 7 days, 8 to 14 days, 15 to 28 days and up to day 181 following vaccination by SOC, PT, relatedness, and severity

- Solicited Rheumatologic AEs within 28 days and up to day 181 following vaccination by Solicited Term and severity
- Solicited Dermatologic AEs within 28 days and up to day 181 following vaccination by Solicited Term and severity
- SAEs up to day 181 by SOC, PT and relatedness
- MAAEs up to day 181 by SOC, PT and relatedness

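### SAP 3.10 sets incomplete AE onsets to the treatment date without looking at the stop date, so an event that ended before vaccination can be tabulated as treatment-emergent

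*SAP*

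**What the plan says.** SAP 3.10 has three branches that end at the treatment date.

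- Day missing, same month and year as treatment: "In this case, in order to conservatively report the event as treatment-emergent, the onset date will be assumed to be the date of treatment".
- Day and month missing, same year as treatment: "In this case, the event onset will be coded to the day of treatment in order to conservatively report the event as treatment-emergent".
- No onset date at all: "A missing onset date will be coded as the day of treatment".

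Partial dates in another month or year go to the first of that month or to 1 January. The stop date appears in none of the branches.

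The AE database starts before dosing. The protocol states this in section 1.5.1 ("AEs will be recorded starting with Screening") and in footnote 5 to the Schedule of Events ("AEs will be recorded beginning with Screening"). Protocol 5.1.1 puts screening 28 to 1 days before dosing. Protocol 5.1.2 lists, among the steps before the injection, "Review of any AEs (including concomitant medications) since previous visit".

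SAP 4.4.2 classes an AE as treatment-emergent by its onset relative to study medication. It tabulates by time since vaccination, for example "Unsolicited AEs within 7 days, 8 to 14 days, 15 to 28 days and up to day 181". SAP 4.4.7 does use the end date for medications: one that ended before vaccination is shown as prior, not concomitant. AEs have no matching rule.

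**The concern.** Assigning the treatment date is meant to protect against missing a treatment-emergent event when timing is unknown. If the recorded stop date lies before the injection, timing relative to dosing is known. The event cannot have started or worsened after vaccination, so it is not treatment-emergent under the SAP wording (onset after dosing) or the protocol wording in 3.1.3 (start or worsening on or after vaccination). The rule still makes it treatment-emergent and places it on the day of injection.

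At stake is the count of early unsolicited AEs in groups of 10 vaccinees and 6 placebo recipients. Under SAP 3.12 these tables are also part of the Day 29 interim analysis, which guides dose selection for the next trial. The record would contradict itself as well, with an onset after its own end.

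**Working it through.** **1. The plan's own figures.** The point disputes no stated number. The nearest are the safety bounds in SAP 3.1. With no events, the exact (Clopper-Pearson) 95% upper limit is 1 − 0.025^(1/n).

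- n = 10: 1 − 0.025^(1/10) = 30.85% (plan: 30.9%).
- n = 30: 1 − 0.025^(1/30) = 11.57% (plan: 11.6%).

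Both agree within rounding.

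**2. The rule applied to one event.** The dates are assumed, chosen to fit the screening period of December 2023 to March 2024 in Protocol Figure 1. Dosing is on 15 January 2024. An AE has onset January 2024 with day unknown, and stop date 10 January 2024.

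- The month and year match treatment, so imputed onset = 15 January.
- Days since vaccination = 0, so the event is treatment-emergent and falls in the 7-day window.
- Duration = stop − onset + 1 = 10 − 15 + 1 = −4 days.
- With a stop-date check, the event stays pre-dose.

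**3. How far each branch reaches.** I took every possible true onset day from 28 days before dosing and counted the pre-dose days that the rule moves to the treatment date.

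| Branch | Dosing 15 Jan 2024 | Other assumed dosing dates |
|---|---|---|
| Day missing | 14 | mean 14.6, range 0 to 28 (1 Jan to 31 Mar 2024) |
| Day and month missing | 14 | 2 (3 Jan), 28 (15 Feb) |
| Wholly missing | 28 | 28 |

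These are calendar days exposed to the rule, not expected events. The error arises only where the AE also has a stop date before dosing.

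**4. Effect of one such event.** Suppose it is the only event of its type in the group. For x = 1 the exact limits are 1 − 0.975^(1/n) and the 97.5% quantile of Beta(2, n − 1).

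| Group | With stop-date check | As written |
|---|---|---|
| One dose, n = 10 | 0/10 = 0% (0% to 30.85%) | 1/10 = 10% (0.3% to 44.5%) |
| All vaccinees, n = 30 | 0/30 = 0% (0% to 11.57%) | 1/30 = 3.3% (0.1% to 17.2%) |
| Placebo, n = 6 | 0/6 = 0% (0% to 45.9%) | 1/6 = 16.7% (0.4% to 64.1%) |

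**5. Conditional illustrations only.** Assume dosing days uniform over a 30-day month and screening lags uniform over 1 to 28 days. Then 434 of 840 combinations (52%) put the screening day in the dosing month. For a post-dose event with only the day missing, and onset uniform over the rest of the dosing month, 39% begin more than 7 days after dosing and the mean shift is 7.3 days. An undated event that truly began at Day 181 would shift by 180 days. None of these is an error rate.

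**The case against.** The strongest defence is that the default is deliberate, ordinary and rarely used. SAP 3.10 twice calls it conservative. AEs are reviewed before the injection, discrepancies are queried (Protocol 3.9), and queries are resolved before the interim freeze (SAP 3.12). Recorded data stay in the listings. Escalation rests on the review committee's look at Day 8 data, not on these tables. An event that ended before dosing would presumably be judged not related, so rows for related events should be untouched.

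Most of this stands and limits the size of the problem. It does not justify the rule where the stop date settles the question, because no ambiguity remains to be conservative about. The Memory Aid gives little help here: it is handed out after the injection and does not cover the screening period. Listings make the error traceable but do not correct the tables.

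A reader might infer three stronger points that the documents do not support.

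- *That arthritis and rash are drained from their late windows.* The dedicated rheumatologic and dermatologic tables in SAP 4.4.2 use one 28-day window and one to Day 181, so a shift inside the first 28 days changes no cell there. The split at 7, 14 and 28 days applies only to unsolicited and solicited neurological AEs. Solicited local and systemic AEs have two windows. Joint and skin terms are also on the systemic list, so a limited effect is possible in that table.
- *That the symptom score is materially distorted.* It takes only solicited local and systemic AEs starting within 14 days, the period of daily diary entries. A pre-dose event would not normally be among them.
- *That late-reported events can always be bounded by the reporting visit.* No section says that the AE form records the visit of first report or absence at earlier visits. Under Protocol 5.4, incomplete Memory Aids are replaced by recollection.

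**Conclusion.** The concern holds in a narrow form. In all three branches, an AE with an incomplete onset date and a stop date before vaccination is misclassified as treatment-emergent and placed in the 7-day window. This follows from the text without any distributional assumption, and no other section corrects it.

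The likely number of such events is small and cannot be estimated from the documents. It needs a healthy volunteer to have an AE that both began and ended before dosing, with a known end and an incomplete start. The consequence per event is one tenth of a dose group's incidence, most likely in the rows for unrelated events. This is a minor correction, worth making because the rule gives a demonstrably wrong answer and the remedy is almost free. For events whose timing relative to dosing is truly unknown, the treatment-date default is reasonable and should stay.

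**What to change.** Add two sentences to SAP 3.10, stated to apply to all three treatment-date branches:

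1. An AE whose full or partial stop date is unambiguously before vaccination is not treatment-emergent, whatever the imputation rule would give.
2. An imputed onset date may not be later than the stop date.

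A partial stop date counts as unambiguous only if its latest possible value precedes vaccination. For example, a stop in December 2023 with dosing in January 2024 qualifies; a stop in the dosing month with the day unknown does not. All other incomplete onsets keep the present default. This brings AEs into line with the end-date logic that SAP 4.4.7 already applies to medications.

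Optionally, where the database records the visit at which an event was first reported, use it to bound the onset of late-reported events, or show them in a row for unknown onset window. They remain treatment-emergent either way.

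The cost is a short SAP edit and one programming condition. No visit, procedure or form changes, provided that the AE form captures a stop date. The duration used in the SAP 4.4.2 symptom index implies that it does. If interim tables have already been run under the present rule, rerun the unsolicited AE tables and note any event that changes class.
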